Negative Affectivity: The negative affect subscale of the 20-item Positive and Negative Affect Schedule (PANAS; Watson et al., 1988) will be utilized to measure negative affectivity. This instrument has shown good internal consistency as well as discriminant and convergent validity (Watson et al., 1988). The PANAS will be administered at all time points to obtain levels of negative affect.

Other Substance Use: In addition to cannabis, Timeline Follow-Back (TLFB; Sobell & Sobell, 1992) will also be used to assess past 3 month use of caffeine, alcohol, tobacco, and illicit drug use during the baseline assessment, and use during weekly assessments and during the 2-week, 4-week, and 6-month post-cessation follow-ups.

Pharmacotherapy Use: The use of pharmacotherapy will be assessed using the prescription medication index (PMI). This measure assesses *class of medication (SSRI/SNRI, benzo, non-benzo hypnotic, trazodone, prazosin, atypical anti-psychotic), dosage, and use since the previous assessment. It is reasonable to expect that the distribution of these prescriptions will not differ across treatment arms after randomization. For classes that do differ, dummy codes will be generated and used in exploratory analyses to evaluate the moderating role of pharmacotherapy on outcomes.*

Table 1. Overview of assessment to be administered at each time point.

		Time Points of Administration
--	--	-------------------------------

Construct	Assessment	Baseline	Weekly During Group	Post- group	2-weeks post-quit	4- weeks post- quit	6-month post-quit
Descriptive Characteristics of the Sample							
Demographics	Demographics	X					
Psychiatric Diagnoses	SCID-I	X					X
Inclusionary/Exclusionary Criteria							
Insomnia Disorder	SCID-I*	X					X
Suicide	SCID-I	X					
Cannabis Use Disorder	SCID-I*	X					X
Motivation to Quit	CL	X					
Sleep apnea	Berlin/PSG	X					
Outcomes: Sleep							
Insomnia Symptoms	CSD	X	X	X	X	X	X
	ACT	X		X	X	X	X
Outcomes: Cannabis Use							
Cannabis Use Frequency	TLFB	X	X	X	X	X	X
Relapse Status	TLFB				X	X	X
Potential Confounding Factors							
Age	Demographics	X					
Era of Service	Demographics	X					
Psychological Diagnosis	SCID-I*	X					
Anxiety Symptoms	IDAS	X		X	X	X	X
Depression Symptoms	IDAS	X		X	X	X	X
Negative Affect	PANAS	X		X	X	X	X
Other Substance Use	TLFB	X	X	X	X	X	X
Pharmacotherapy	PMI	X	X	X	X	X	X

Note: * = modified to be consistent with DSM-5 criteria. The post-group assessment corresponds to completion of the treatment/placebo groups.

2a.3.j. Planned Data Analysis.

Generalized Linear Mixed Modeling (GLMM) will be used as the primary data analytic approach for Aims 1 and 2. We believe this approach will provide the most parsimonious test of our hypotheses based on the following considerations. First, we considered only evaluating outcomes at the 6-month follow-up. While this approach would provide information regarding long-term outcomes, it has significant limitations including: (a) increased potential for attrition and missing data, and (b) loss of knowledge regarding outcomes immediately after the quit attempt (i.e., 2-weeks, 4-weeks). For these reasons an analysis focusing solely on the 6-month follow-up would not provide the most reliable and powerful test of the hypotheses. Second, *GLMM allows for modeling slope and change over time. This approach will allow us to model change in substance use and sleep over the course of short-term (2-weeks, 4-weeks) and long-term (6-months) follow-up, while also allowing us to model any unpredicted change in substance use (e.g., cannabis) during the treatment/placebo phase.* Based on these considerations we opted to conduct the primary analysis for Aims 1 and 2 by evaluating change over time through the use of GLMM. This analytic approach is favorable for a number of reasons including its ability to include all available data, not just data from patients who complete assessments. In addition, we will conduct secondary analyses for each hypothesis to evaluate group differences at each time point.

To account for family wise error, alpha will be adjusted in all secondary analyses. *Importantly, over the course of group CBT-I (or placebo group), we will track participants' substance use, including cannabis, and sleep. We will model all outcome data from the start of the intervention. This approach will allow for modeling any unpredicted changes in cannabis use (i.e., increase or decrease in use) during the intervention portion of the study.* Below we provide a detailed overview of how GLMM will be employed for Aims 1 and 2.

Aim 1:

Hypothesis 1.1. Veterans who receive either *CBT-I-MA* or *CBT-I* prior to a cannabis cessation attempt will evidence a greater reduction in cannabis use frequency over the three post-quit attempt assessments (2-weeks, 4-weeks, and 6-months post-quit day) as compared to those who receive *PC*. In order to test this hypothesis a mixed-effects regression will be used to model changes in the dependent variable (frequency of cannabis use) across time as a function of group membership and baseline values (fixed effects) with a random effect for person to account for repeated measurements; frequency of cannabis use (obtained from TLFB; See 'measures' section for details).

As a secondary analysis, we will conduct an *analysis of covariance (ANCOVA; alpha set to .01)* to examine group differences in cannabis use frequency at each time point (2-weeks, 4-weeks, and 6-months post-cessation).

Hypothesis 1.2. Veterans receiving either *CBT-I-MA* or *CBT-I* will have greater point prevalence abstinence (PPA) over the three post-quit attempt assessments (2-weeks, 4-weeks, and 6-months post-quit day) compared to those receiving *PC*. In order to test this aim we will evaluate the differences in PPA between *CBT-I-MA* and both *CBT-I* and *PC* groups, and *CBT-I* and *PC* groups across the three follow-up assessments (2-weeks, 4-weeks, and 6-months post-cessation). This will be conducted through the use of a mixed-effects logistic regression.

As a secondary analysis, we will conduct three chi-square analyses to examine group differences in rates of PPA at each of the three time points (2-weeks, 4-weeks, 6-months post-cessation).

Exploratory Hypothesis. *In terms of the above cannabis outcomes, those who receive CBT-I-MA will evidence better outcomes (reduced frequency and greater PPA) as compared to those who receive CBT-I. Results related to this hypothesis will be determined through analyses conducted for the primary hypotheses (Hypothesis 1.1 and 1.2).*

Secondarily, we will conduct exploratory analyses to examine factors (e.g., adherence, dose) that account for differences observed between the *CBT-I-MA* and *CBT-I* groups in relation to cannabis outcomes through the use of mediation models. Mediators of interest will include adherence (measured by session attendance), and dose.

Aim 2:

Hypothesis 2.1. Veterans who receive either *CBT-I-MA* or *CBT-I* prior to a cannabis cessation attempt will evidence improved sleep quality, as indicated by self-report and objective measures, over the three post-quit attempt assessments (2-weeks, 4-weeks, and 6-months post-quit day) as compared to those who receive *PC*. In order to test this hypothesis, two mixed-effects regressions will be conducted, one for self-report sleep (see 'measures' section for details) and another for objective indices of sleep (see 'measures' section for details). First, we will model changes in the dependent variable (self-report or objective sleep) across time as a function of group membership and baseline values (fixed effects) with a random effect for person to account for repeated measurements (random effects).

As a secondary analysis, four ANCOVAs will be conducted to examine differences in self-reported sleep quality between groups at each time point (following 6-week treatment/placebo group, 2-weeks, 4-weeks, 6-months post-cessation attempt). A series of four additional ANCOVAs will then be conducted to examine group-based differences in objective sleep at each time point (following 6-week treatment/placebo group, 2-weeks, 4-weeks, 6-months post-cessation attempt). All ANCOVAs will adjust alpha to account for family wise error rate.

Hypothesis 2.2. *Group based differences in cannabis outcomes averaged across the three post-quit attempt assessments (2-weeks, 4-weeks, and 6-months post-quit day) will be explained*

by average sleep quality (self-report and objective) averaged across the three post-quit attempt assessments. To address the second hypothesis of aim 1, GLMM will be used to evaluate the mediating role of (a) self-report sleep quality averaged over time (b) objective sleep quality over time (2-week, 4-week, and 6-month post-cessation follow-ups). The MacArthur model of mediation will be used as this model, compared to Baron and Kenny's approach, is not based on a linear model. In addition the longitudinal design allows for determination of the temporal precedent of our mediator to the predictor variable, thereby meeting criteria for the MacArthur approach (Kraemer et al., 2008). Specifically, two independent models will be conducted. First, we will evaluate self-report sleep quality over time on the relation between group and average cannabis use frequency over time. Three steps will be conducted using mixed models. First, we will examine the relation between group and cannabis use frequency over time (path C). Second, we will examine the relation between group and self-reported sleep quality over time (path A). Finally, we will enter both group and self-reported sleep quality over time within the same model to predict frequency of cannabis use over time. Confidence intervals will be used to assess for significant partial mediation. Within the mediation model, the same series of steps will be conducted to evaluate the mediating role of objective sleep over time on the relation between group and cannabis use frequency over time.

Exploratory Hypothesis. *In terms of the above sleep outcomes, those who receive CBT-I-MA will evidence better outcomes (improved sleep quality) as compared to those who receive CBT-I. Results related to this hypothesis will be determined through analyses conducted for the primary hypothesis of Aim 2 (Hypothesis 2.1).*

Secondarily, we will conduct exploratory analyses to examine factors (e.g., adherence, dose) that account for differences observed between the CBT-I-MA and CBT-I groups in terms of sleep outcomes through the use of mediation models. Mediators of interest will include adherence (measured by session attendance), and dose.

In the event that groups differ in terms of potential confounding factors (e.g., psychological conditions, pharmacotherapy) exploratory analyses will be conducted to investigate these factors as moderators of the outcomes. Should moderation be demonstrated (i.e., significant effect size), we will use this information to formally power the next study to specifically test for these factors (Kraemer et al., 2002).

Power Analysis.

For this study, our primary aims are to investigate the impact of CBT-I-MA and CBT-I (compared to PC) on (a) frequency of cannabis use and PPA, and (b) self-reported and objective indices of sleep. We expect that group based differences in cannabis outcomes will be partially attributable to sleep. *In addition, we expect that CBT-I-MA will evidence better outcomes compared to CBT-I. Exploratory analyses will examine factors that may account for these differences.*

Existing empirical work has established medium to large effect sizes for the effect of therapist administered CBT-I on sleep outcomes among individuals with psychiatric comorbidities (Cohen's d's range from 0.56 – 2.20; Smith et al., 2005). *While no research has examined the effect size of CBT-I with an adjunctive mobile app, previous research has demonstrated a small/medium sized effect (Cohen's d's = 0.42) to observe differences in outcomes between treatment as usual for substance use disorders and treatment as usual with a technology-based adjunctive component (McKay et al., 2010).* In addition, no research has examined the impact of CBT-I on cannabis use outcomes. However, previous work has demonstrated that sleep disturbances resulting from withdrawal from cannabis use are attenuated through sleep interventions (Cohen's d's range from 1.4-2.4; Vandrey et al., 2011).

Based on these established effects, we conducted a power analysis to determine the necessary sample size to detect the hypothesized effects. To begin, power calculations were based on the hypothesis related to tests of mediation on the relation between group and sleep outcomes, as this would require the greatest sample size to detect the established effect size given the required analyses. Based on established methods to calculate power for mediation, *a sample of 168 Veterans would be required to detect a small/medium mediation effect with a power of .80 and alpha of .05*. This sample size would allow for the ability to detect the additional expected effects for Aims 1 and 2.

In terms of the primary hypothesis of Aim 1 (Hypothesis 1.1), *the impact of CBT-I-MA and CBT-I on frequency of cannabis use post-cessation, we based our power calculations on an ANCOVA with the inclusion of 3 covariates as this would provide an overestimation of the sample size required for the GLMM analysis. A sample of 168 individuals would allow for a detection of a significantly smaller effect in terms of the primary aim ($d = .42$), providing confidence in our ability to detect the hypothesized effect of $d = 1.4$. This sample size will also allow for adequate power to detect group differences between CBT-I-MA and CBT-I ($d = .42$; Aim 1 Exploratory Hypothesis)*.

In terms of the secondary hypothesis of Aim 1 (Hypothesis 1.2), *the impact of CBT-I-MA and CBT-I on PPA, we used power calculation software to calculate the effect size based on a test of independent proportions. With an estimated abstinence rate of 20% within the placebo condition (PC; based on previous research; Marijuana treatment project research group, 2004), and alpha of .05, 168 Veterans (56 per group) will allow for power of .80 to detect a 30% difference in the prevalence of abstinence in the CBT-I group. As we conservatively estimate a 50% abstinence rate in the CBT-I condition, we will have enough power to detect the expected effect*.

In terms of Aim 2, investigating the role of CBT-I-MA and CBT-I on subjective and objective sleep quality, *we based our power analysis on an ANCOVA with the inclusion of 3 covariates and 3 groups as this would overestimate the required sample size needed within GLMM models. A sample of 168 individuals would allow for a detection of a smaller effect in terms of the primary aim ($d = .42$), providing confidence in our ability to detect the hypothesized conservative effect of $d = .56$. This will also allow for adequate power to detect group differences between CBT-I-MA and CBT-I ($d = .42$; Aim 2 Exploratory Hypothesis)*.

Therefore a total sample of 168 will be adequate to detect all expected effects. An intent-to-treat approach will also be used. Therefore, all individuals randomized will be included in analyses. In the event that a set of individuals do not receive a minimum intervention dose (i.e., attend 70% of group sessions; Litt et al., 2007; Project Match Research Group, 1997), we will conduct analyses with and without these individuals. This sample size is feasible over the course of 4 years as evidenced in previous work conducted among outpatient substance use research protocols (Heinz et al., 2013).

Missing Data. Based on our protocol to limit participant attrition, we expect relatively little missing data over the 6 months of this study. We will limit the effect of missing data both methodologically and statistically. *First, we will account for 10% loss prior to randomization. Therefore, we will aim to recruit 187 individuals, with the goal of randomizing 168 individuals for the intent-to-treat analyses. Second, we chose to model our data using a GLMM approach as this method allows for multiple missing data points within longitudinal designs making this a robust analytic method for handling missing data. Additionally, as it is likely that not all participants will be included in analyses due to missing data, we will examine the reliability of the results by re-conducting analyses on complete data sets obtained through multiple imputation procedures and pooling*

results (Graham, 2012). Sensitivity analysis will then be conducted to examine the impact of missing data on outcomes (Carpenter et al., 2007).

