Participant retention strategies are based on strategies successfully used in past research designs by members of this research team. Based on previous prospective designs, the risk for participant attrition may occur at 3 main time points: baseline, during treatment, and follow-up. We will specifically address each time point to limit attrition rates. First, it is expected that a small number of individuals will not complete the baseline assessment. In this case, those individuals will be excluded from data analysis and replaced with another participant. In relation to prospective retention, of those completing baseline procedures, we expect 80% of the original sample to complete all follow-up assessments (Heinz et al., 2013; also see section 2a.3, “Missing Data” subsection). *We will recruit 187 Veterans in order to account for 10% attrition from baseline to the group intervention, with the goal of randomizing 168 Veterans.* In addition, an intent-to-treat approach will be used for all analyses. *Within the intent-to-treat approach individuals completing at least 70% of the intervention/control group will be included in all analyses, thereby limiting the impact of the predicted 20% attrition.* Finally, we will employ a multi-pronged approach to enhance participation in all follow-up assessments. This approach will utilize financial incentives, participant contact, and session reminders.

Financial Incentives. To reduce attrition rates, a weighted compensation schedule will be employed as follows: Baseline assessment (\$50), post-treatment/placebo group (6-weeks) (\$50), 2-weeks post-cessation (\$25), 4-weeks post-cessation (\$25), and 6-months post-cessation (\$25), with a \$60 bonus for individuals that completed all time points. Overall, the rate of compensation was determined based on \$19/hour of daytime assessment.

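### The SAP puts a 70% attendance condition inside intent-to-treat in one place, includes everyone randomised in another, and never names the primary set

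*SAP*

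**What the plan says.** Two places in the SAP describe who is analysed under intent-to-treat.

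- **Section 2a.3.f, Participant Retention.** Having said that intent-to-treat applies to every analysis, the SAP adds: "Within the intent-to-treat approach individuals completing at least 70% of the intervention/control group will be included in all analyses". It gives the purpose as "thereby limiting the impact of the predicted 20% attrition".
- **Power Analysis, closing paragraph.** Intent-to-treat is used again, with a different consequence: "Therefore, all individuals randomized will be included in analyses". If some participants fall short of a minimum dose, defined as attending 70% of group sessions, "we will conduct analyses with and without these individuals". Neither run is called primary, secondary or sensitivity.

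Other parts bear on the point without defining an analysis set:

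- Section 2a.3.j (Planned Data Analysis) favours the mixed model for "its ability to include all available data, not just data from patients who complete assessments".
- The Missing Data paragraph sets recruitment "with the goal of randomizing 168 individuals for the intent-to-treat analyses".
- The power statement for Hypothesis 1.2 reads "168 Veterans (56 per group) will allow for power of .80 to detect a 30% difference in the prevalence of abstinence".

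The model descriptions for Aims 1 and 2 name no analysis population, and the protocol text provided does not define one either.

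**The concern.** If everyone randomised is analysed, the 70% condition in 2a.3.f does nothing. If it does something, it selects participants on attendance, which is observed only after randomisation. The two rules share one name and can give different data sets.

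Such selection matters if attendance, or the link between attendance and outcome, differs by arm. The arms receive different content: CBT-I with sleep restriction, the same with a mobile app, or quasi-desensitisation. Equal attendance therefore cannot be taken for granted. The SAP itself lists session attendance as a candidate mediator, although only for CBT-I-MA versus CBT-I. An attender-only comparison with placebo would lose the protection of randomisation, could be biased either way, and would rest on fewer than the 56 per group used for power.

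The second gap is smaller. The Power Analysis paragraph would keep everyone, but the reader has to infer which of its two runs leads.

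**Working it through.** **Inputs from the SAP**

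- Six weekly sessions and a 70% threshold.
- 187 recruited and 168 randomised, 56 per group.
- 20% abstinence on placebo and a planned 30-point difference.
- For Hypothesis 1.1, a detectable d = .42, with the SAP "providing confidence in our ability to detect the hypothesized effect of" d = 1.4.
- For Aim 2, a conservative d = .56.

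These effect sizes are taken as stated. The SAP gives no attendance rates.

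**The plan's own figure.** 168 / 0.9 = 186.7, rounded up to 187; 187 × 0.9 = 168.3. The figure reproduces, and it shows that 168 is a randomised number with no allowance for removing low attenders.

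**The threshold.** 0.7 × 6 = 4.2 sessions. Four of six is 67% and five of six is 83%, so the condition means at least 5 of 6.

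**Bias illustration, abstinence (assumptions mine).** There is no true effect, and abstinence is 20% in both arms. Let e be the share of an arm below the threshold and q the abstinence rate among them. Abstinence among those kept is (0.20 − e·q)/(1 − e). With q = 0.05 in both arms:

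| e, CBT-I / PC | Kept, CBT-I | Kept, PC | False difference | Share of 30 points |
|---|---|---|---|---|
| 20% / 20% | .2375 | .2375 | 0 | 0 |
| 22.5% / 17.5% | .2435 | .2318 | 1.2 points | 4% |
| 25% / 15% | .2500 | .2265 | 2.4 points | 8% |
| 30% / 10% | .2643 | .2167 | 4.8 points | 16% |

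Swapping the shares reverses the signs. Equal attendance does not guarantee safety: with e = 20% in both arms but q = 5% versus 15%, the difference is .2375 − .2125 = 2.5 points (8%).

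**Bias illustration, frequency of use (assumptions mine).** Set each arm's mean to 0 and let low attenders be worse by D. The mean among those kept is −e·D, so the size of the bias is |e1 − e2| × D. With D = 0.5 SD:

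| Gap in e | Bias (SD) | Share of d = .42 | Share of d = 1.4 |
|---|---|---|---|
| 0 | 0 | 0 | 0 |
| 5 points | 0.025 | 6% | 2% |
| 10 points | 0.05 | 12% | 4% |
| 20 points | 0.10 | 24% | 7% |

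The direction can be either.

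**Sample illustration.** If 10%, 20% or 30% fell below the threshold, 56 × 0.9 = 50.4, 56 × 0.8 = 44.8 or 56 × 0.7 = 39.2 per arm would remain.

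Power at two-sided alpha .05 (sidedness is my assumption), by normal approximation:

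- Proportions: Φ[(0.30√n − 1.96√(2 × .35 × .65)) / √(.2 × .8 + .5 × .5)].
- Means: Φ[d√(n/2) − 1.96].

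| n per arm | 20% vs 50% | Pairwise d = .56 |
|---|---|---|
| 56 | 92.5% | 84.2% |
| 44.8 | 85.8% | 75.5% |
| 39.2 | 80.7% | 69.8% |

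The 92.5% is above the .80 that the SAP states for 56 per group. That is a separate matter and does not affect this point.

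**The case against.** The strongest reply is that 2a.3.f excludes nobody. It says who will be included, without the word only, and its stated aim is to limit the effect of attrition. Dropping low attenders would defeat that aim, so the sentence may mean only that attenders who miss follow-up are kept. It also sits in a section on retention, whereas the analysis text commits to all randomised. The with-and-without runs come after that unconditional rule and apply only if some participants miss the minimum dose, so they read naturally as sensitivity analyses.

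Much of this stands. The plan as a whole does favour all randomised, and the benign reading is plausible. It does not remove the conflict: the sentence ties inclusion in every analysis to a completion threshold and, even read kindly, is silent on randomised people below it.

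The size can also be challenged. Every bias figure rests on assumed attendance, zero is among the results, and the most uneven split shown gives 4.8 points against 30. For 20% versus 50%, power stays above .80 even with 30% removed. That is fair, although power for d = .56 falls below .80 once 20% are removed.

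Last, the Missing Data paragraph expects some participants to drop out of analyses because of missing data, which sits awkwardly beside a rule that includes everyone. The two can coexist. Using all available outcome data regardless of attendance leaves missing outcomes to the mixed model and the planned multiple imputation and sensitivity analyses.

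**Conclusion.** The concern holds and should be fixed. The SAP contains two incompatible inclusion rules under one name, and it does not say which of its two planned runs is primary. The contradiction rests on the text alone. Its consequence cannot be sized from the documents: under the assumptions shown, the false difference runs from 0 to 4.8 points of abstinence, or 0 to 0.10 SD of use frequency, in either direction. The loss of 10% to 30% of each arm is likewise assumed, and it arises only if the attendance condition is applied. Because the rest of the plan already leans towards all randomised, this corrects a stray rule and leaves the design as it is.

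**What to change.** 1. In section 2a.3.f, delete the sentence with the 70% condition and put the all-randomised rule from the Power Analysis closing paragraph in its place.
2. State that the primary analysis for Aims 1 and 2 includes every randomised participant, whatever number is achieved, in the arm assigned, using all available outcome data regardless of attendance.
3. In the Power Analysis closing paragraph, label the run without participants below 70% attendance (fewer than 5 of 6 sessions) as supplementary.

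The Missing Data paragraph needs no change. The cost is SAP wording in two places. The planned 168 is unchanged, and no new data or procedures are needed. If CBT-I works, the effect estimated in all randomised participants may be somewhat smaller than among attenders, because it includes people who received less of the intervention. That is separate from the selection bias illustrated under no effect, whose direction is unknown.

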Cannabis Use Frequency and Relapse: Timeline follow-back (TLFB; Sobell & Sobell, 1992) will be used to assess past 3 month cannabis use at baseline and at the 2-week, 4-week, and 6-month follow-ups. The TLFB procedure has demonstrated good reliability and validity in past work across diverse samples (Sobell & Sobell, 1992). Cannabis use information obtained from the TLFB will be used as outcome variables for Aim 1. Research has demonstrated that TLFB is as effective as biochemical measures of substance use (Hjorthøj et al., 2012; Hjorthøj, Fohlmann, et al., 2012).

Measures: Sleep Disturbance.

Sleep Diary: The Consensus Sleep Diary (CSD; Carney et al., 2012) will be used to prospectively monitor self-reported sleep. The sleep diary has been deemed the "gold standard" self-report assessment of sleep (Carney et al., 2012). The CSD is a new standardized sleep diary based on expert consensus and qualitative patient input, developed for use across a range of clinical and research settings. The CSD is the primary self-report sleep assessment being used to monitor responses to CBT-I within the VHA roll-out of this treatment. The CSD will be completed daily throughout the course of this study.

Objective Sleep Assessment: Lab-Based Polysomnography (PSG): Lab-based overnight polysomnography will be conducted through the use of the Nihon Kohden Trackit Sleepwalker system to objectively measure sleep and assess for severity of sleep apnea (AHI) during the baseline assessment. This system is a 16-channel, level 2 ambulatory monitoring system that acquires the following signals: EEG (at F3, F4, Cz, Pz), horizontal electroculogram (EOG), chin electromyogram (EMG), Electrocardiogram (ECG), chest circumference (impedance plethysmography), abdominal circumference, nasal pressure, left and right leg movement (via accelerometry), oxygen saturation (SpO₂), and body position (right lateral, left lateral, prone, and supine). Based on these signals we will obtain data on obstructive sleep apnea, sleep staging, body position, total sleep time, and sleep efficiency. Assessment will take place within the sleep

lab of the NCPTSD.

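### Cannabis use frequency (H1.1): a 3-month recall window at the 2- and 4-week visits, with no scoring rule, would dilute the post-quit effect

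*SAP*

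**What the plan says.** SAP section 2a.3.i, Measures: Cannabis Use, states that the TLFB "will be used to assess past 3 month cannabis use at baseline and at the 2-week, 4-week, and 6-month follow-ups". The same paragraph makes the TLFB the source of the Aim 1 outcome variables.

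Hypothesis 1.1 predicts a "greater reduction in cannabis use frequency over the three post-quit attempt assessments". It defines the outcome as "frequency of cannabis use (obtained from TLFB" and sends the reader back to the measures section. Its secondary analysis compares the groups visit by visit ("ANCOVA; alpha set to .01").

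Other parts of the SAP bear on the window:

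- The Power Analysis for Hypothesis 1.1 speaks of the impact "on frequency of cannabis use post-cessation".
- Other Substance Use attaches the 3-month period to baseline only: "past 3 month use of caffeine, alcohol, tobacco, and illicit drug use during the baseline assessment, and use during weekly assessments".
- Table 1 schedules cannabis TLFB weekly during the groups and at the post-group visit. The Cannabis Use paragraph does not mention these records.
- Section 2a.3.j says "we opted to conduct the primary analysis for Aims 1 and 2 by evaluating change over time through the use of GLMM", and also "We will model all outcome data from the start of the intervention".

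The 2015 protocol times the follow-ups from the end of treatment and gives no window for cannabis frequency. The TLFB form is an attachment that cannot be seen here.

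**The concern.** The only window written for the H1.1 outcome reaches back well before the quit day at the first two follow-ups. No sentence gives a denominator or limits the count to days after quitting. A 3-month count taken 2 or 4 weeks after quitting cannot be a measure of use after cessation.

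If the window is scored as written, the early values mix post-quit days with treatment days and with days before treatment began. The pre-treatment days cannot carry an effect, and they may also sit in the baseline covariate. At stake are the size of the effect at 2 and 4 weeks, the size of the averaged contrast, and how the time course is read.

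**Working it through.** The plan states no share of post-quit days, so there is no figure to reproduce.

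**Inputs**
- Window: 3 months (SAP, Measures: Cannabis Use), taken as 91 days; 84 to 92 days also tried.
- Visits: 14, 28 and about 182 days after the quit day (SAP, Hypothesis 1.1). The quit day follows the week-6 assessment, so the protocol's post-treatment timing gives essentially the same counts.
- Group phase: 6 weeks = 42 days (SAP, Data Collection Procedures). Groups are assumed to start right after baseline.

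**Days in each 91-day window.** Share for an effect from the quit day = min(days since quit, 91)/91. Share for an effect in full from group start = min(days since quit + 42, 91)/91.

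| Visit | Post-quit | Treatment | Pre-treatment | Share, from quit | Share, from group start |
|---|---|---|---|---|---|
| 2 weeks | 14 | 42 | 35 | 14/91 = 15% | 56/91 = 62% |
| 4 weeks | 28 | 42 | 21 | 28/91 = 31% | 70/91 = 77% |
| 6 months | 91 | 0 | 0 | 100% | 100% |
| Mean | | | | 49% | 79% |

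With 84 to 92 days, the post-quit shares are 15-17%, 30-33% and 100%. The 2- and 4-week windows share 91 − 14 = 77 of 91 days (85%).

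**Effect on a constant difference.** A true 10-point post-quit difference would read 1.5, 3.1 and 10 points (onset at quit) or 6.2, 7.7 and 10 (onset with the intervention). The averages are 4.9 and 7.9, so about 50% and 20% too small.

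**Windows cut at the start of the intervention.** For an effect from the quit day the shares would be 14/56 = 25%, 28/70 = 40% and 100%. For an effect in full from group start they would be 100% throughout, and the artefact disappears.

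**Illustrative simulation.** All inputs are assumed:
- 56 per arm, 2,000 runs; one active arm against placebo control unless stated.
- The median person uses on 80% of days before; afterwards 60% (control) or 45% (active), constant after quitting.
- Person SD 1.0 and change SD 1.0 on the logit scale; days independent given the person.
- Adjustment for the baseline proportion.

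Each cell shows 91-day windows against post-quit scoring (days 1-14, 15-28 and 92-182).

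| Quantity | Onset at quit | Onset with intervention |
|---|---|---|
| Averaged contrast, estimate | −.054 vs −.110 | −.088 vs −.111 |
| Averaged contrast, power at .05 | .77 vs .80 | .83 vs .82 |
| 6-month minus 2-week group difference, rejections at .05 | 80% vs 5% | 64% vs 5% |
| Three-group ANCOVA at .01, 2 weeks, power | .17 vs .51 | .61 vs .50 |
| Three-group ANCOVA at .01, 4 weeks, power | .40 vs .52 | .63 vs .50 |

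With 45 per arm (80% retention), averaged-contrast power is .65 vs .68 and .72 vs .70. With no group effect, the 6-month-minus-2-week test rejects in 5-6% of runs under either scoring. With windows cut at the start of the intervention, it rejects in about 4% of runs (onset with intervention, no dilution) or about 76% (onset at quit).

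**The case against.** The strongest reply is that the Cannabis Use paragraph describes what is recalled, not what is scored. It never says that the outcome is a 3-month total. The Power Analysis names use after cessation. The parallel paragraph on other substances limits the 3-month period to baseline. Table 1 collects treatment-phase days weekly, so a 3-month follow-up count would include those days a second time. The sentence on modelling from the start of the intervention may also exclude pre-treatment days, if it refers to days and not to records. If TLFB is kept day by day, nothing is lost in collection.

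All of this is fair, and the wording may simply be loose. What stands is that it is the only window given for this outcome and that Hypothesis 1.1 points to it. Even with pre-treatment days removed, an effect that starts at quitting would still be diluted.

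Three further objections hold in full:

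- A reader might infer that the primary test will report a false growing effect. Hypothesis 1.1 lists group and baseline as fixed effects and names no group-by-time term. The stated interest in change over time allows such a term but does not specify it, so the 80% and 64% figures are not for a planned test.
- The 15/31/100% pattern is not the only plausible one. The 2015 protocol drops the motivation-to-quit criterion and expects reduced use to follow the interventions, which makes 62/77/100% at least as plausible.
- A reader might conclude that treatment-phase records should be left out of the model. The SAP gives a reason for including them, and nothing here shows that to be an error.

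**Conclusion.** The point holds, conditionally, and should be fixed. If the 3-month window is scored at every follow-up, a constant post-quit difference is understated at 2 and 4 weeks. The averaged contrast is about 20% too small (onset with the intervention) to 50% too small (onset at quit). If a group-by-time term is fitted, a constant effect would look like a growing one.

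A general loss of power might be inferred, but it is not supported: averaged-contrast power changes by about 3 points at most in the illustrative runs. Clear losses appear only in the secondary 2- and 4-week ANCOVAs, and only for an effect that starts at quitting. Nothing follows for point prevalence abstinence (Hypothesis 1.2), because its window is not defined.

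The shares rest on a 91-day window and a 42-day group phase starting right after baseline. The simulation figures also rest on its assumed inputs. Confidence is medium, because the paragraph may be loose wording and the form is not available.

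**What to change.** Keep the 3-month window at baseline and add one scoring rule to the SAP: H1.1 frequency at each follow-up is the proportion of TLFB days with cannabis use, counted only from days after the quit day (end of treatment under the 2015 protocol) and since the previous follow-up. That means days 1-14, days 15-28, and the last 3 months at the 6-month visit.

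Allow for the unequal numbers of days in the model, for example by analysing days used out of days observed. Keep the weekly treatment-phase TLFB as separate records, as section 2a.3.j plans, and state that the H1.1 contrast is taken over the three follow-ups. Bring the Cannabis Use paragraph, the Other Substance Use paragraph and the Power Analysis into line with this wording.

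The cost is SAP wording and, if TLFB is recorded by day, a rescoring; data collection does not change. The 14-day values are less precise than 91-day ones. If the effect starts with the intervention, 2-week ANCOVA power could be lower (.50 vs .61 in the illustrative simulation). Days 29-91 after quitting, 182 − 91 − 28 = 63 of 182 days (35%), fall in no follow-up window, as is already the case.
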